5.1.3 Unscheduled Visits

During the course of the study, additional contact by telephone call, or unscheduled site visit, (or both) may be considered, based on Investigator's discretion. Assessments completed during these visits (on-site or by telephone call), may include evaluation of SMBG data, insulin doses, AEs (eg, volume depletion, elevated creatinine), hypoglycemic events, etc. The Unscheduled Visit electronic case report form (eCRF) will be completed for each unscheduled telephone contact or site visit.

5.1.4 24-Week Double-blind Treatment Period

Following completion of the single-blind placebo Run-in Period, eligible patients will enter the 24-week, double-blind Treatment Period. Patients will be randomly assigned 1:1 in parallel between the 2 treatment groups: sotagliflozin 400 mg or placebo.

The double-blind Treatment Period includes 5 clinic visits (Baseline, and Weeks 4, 8, 16, and 24).

For all patients, clinic visits should be scheduled in the morning at approximately the same time of day.

In regard to patients taking antihypertensive medications, the Investigator will be asked to maintain dosages unchanged between Baseline and Week 16, if this is consistent with proper medical management of the patient.

For patients in the satiety substudy, the satiety daily diaries completed during the single-blind placebo Run-in Period will be collected at Day 1 (Baseline). At the visit scheduled for Week 16, these patients will receive packets of satiety daily diaries. At the beginning of Week 23, patients will receive a telephone call to remind them to start recording information onto the satiety daily diaries. The patients will be instructed to complete the paper diary each day, before the first meal of the day for the last 2 weeks of the double-blind Treatment Period (ie, during Week 23 and during Week 24, a total of 14 days, ± 3 days). The diaries will be returned to the site at the visit scheduled for the end of Week 24.

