7.6.1.5 Insulin Adjustment Strategy

- The need for insulin adjustments will be evaluated by the Investigator with the goal of maintaining or improving glycemic control consistent with the glycemic target ranges, local SOC, and the individual needs of the patient (see [Section 7.6.1.2](#)).
- Suggested insulin adjustment algorithms are provided in the Site File Notebook to serve as reference, which may be modified based on the Investigator's clinical assessment.
- When insulin is adjusted, it is recommended that any changes be made in increments of 10% or less, as assessed appropriate by the Investigator.
- During the course of the study, increases in insulin that affect the appropriate insulin action time period should be considered if the SMBG pattern or trajectory over 3-5 days is assessed as above the patient's individualized target range, and there is no evidence of hypoglycemia in the insulin-action time period (see [Section 7.6.1.2](#)).
- During the course of the study, decreases in insulin, which affect the appropriate insulin-action time period, should be considered if the SMBG pattern or trajectory is assessed as below the patient's individualized target range.

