^bEffective serum osmolality = $2[\text{Na}^+ \text{ (mEq/L)}] + [\text{glucose (mg/dL)}]/18]$

In the table, anion gap = $[\text{Na}^+] - [\text{Cl}^- + \text{HCO}_3^-]$ with the normal anion gap referenced as “between 7 and 9 mEq/L, and an anion gap > 10-12 mEq/L indicates the presence of increased anion gap metabolic acidosis”. However, the normal range for each of the individual measurements varies depending upon the specific methodology used. In addition, the serum potassium can be included in the anion gap measurement, resulting in a normal range that is approximately 4 mEq/L higher than the number calculated using the preceding equation. As a result, interpretation of the anion gap should be based on the laboratory reference range for the anion gap, and considering baseline values for the individual patient.

Source: Adapted from Kitabchi, 2009 [21]

The therapeutic goals in DKA management include restoration of circulatory volume and tissue perfusion, decreasing serum glucose, clearance of serum ketoacids, and correction of electrolyte abnormalities.

Instructions for the patient and site staff:

At every clinic visit blood BHB (central laboratory and point-of-care) testing will be conducted. At visits where UA is performed, the evaluation will include urine ketone determination by dipstick.

It is possible that GI or other AEs occurring with LX4211 may mask presenting symptoms of DKA (Appendix F). These symptoms include but are not limited to: inability to maintain oral intake, generalized weakness, excessive thirst, abdominal pain, nausea, vomiting, rapid weight loss, fever, frequent urination, fruity-scented breath, confusion, acute illness and/or consistently elevated blood glucose. Therefore, it is important that patients with GI complaints or intercurrent illness be instructed by the site to measure their blood or urine ketone or blood BHB levels.

(Note: In some patients alcohol may be a possible trigger for ketosis).

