Dispense satiety daily diaries and review instruction for use [n]		X				X		
Collect satiety daily diaries [o]			X				X	
Laboratory/glycemic Assessments								
A1C [p]	X	X	X	X	X	X	X	
Fingerstick glucose on site	X	X	X	X	X	X	X	
Fasting plasma glucose [p]	X		X	X	X	X	X	
Fasting serum chemistry [p]	X		X	X	X	X	X	
Fasting lipid profile [p]	X		X		X		X	
BHB (central lab)	X	X	X	X	X	X	X	
BHB (point-of-care)	X	X	X	X	X	X	X	
Hematology	X		X		X		X	
Urine albumin, calcium, glucose, creatinine			X				X	
Urinalysis with microscopy	X		X				X	
Pregnancy test (serum) [q]	X							
Pregnancy test (urine) [q]			X				X	
Follicle stimulating hormone (females only) [r]	X							
Thyroid stimulating hormone [s]	X							
Fasting blood sample and random urine for storage			X				X	

A1C = hemoglobin A1C; ADA = American Diabetes Association; AE = adverse event; BHB = beta-hydroxy butyrate; BP = blood pressure; EASD = European Association for the Study of Diabetes; eCRF = electronic case report form; DKA = diabetic ketoacidosis; ECG = electrocardiogram; EOSI = Events of Special Interest; EOT = End of Treatment; EW = early withdrawal; IXRS = Interactive Voice/Web Response System; SAE = serious adverse event; SMBG = self-monitored blood glucose; Wk = Week

- a. The duration of the single-blind placebo Run-in Period is 14 days, ± 3 days.
- b. All laboratory assessments occur prior to first dose of double-blind study drug. All visit dates will be scheduled based on the date of randomization with a ± 3 days visit window allowed.
- c. All patients will have a follow-up telephone contact 30 days after the last dose of study drug to collect information on any SAEs, any EOSI, or AEs that were ongoing at the time of the EOT/EW Visit.
- d. A complete physical examination will include, at minimum, a review of the patient's general appearance, head, eyes, ears, nose and throat, neck, heart, lungs, abdomen, back and extremities, skin, and general neurological system. A symptom related brief physical exam will only occur if the patient is experiencing symptoms or AEs. If a symptom related brief physical exam is required, it should include a review of all body systems that relate to the symptoms and/or AE the patient is experiencing.
- e. Patients should be weighed at approximately the same time of day, wearing minimal clothing, ie, no coat/shoes, using the same calibrated scale where possible.

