| 2 Week 4 | 29 | 2-43 | -- | -- |
| 3 Week 8 | 57 | 44-85 | -- | 2-113 |
| 4 Week 16 | 113 | 86-141 | -- | -- |
| 5 Week 24 | 169 | ≥142 | ≥2 | ≥114 |

(a) Relative to the date of Baseline/Randomization visit (Day 1)

(b) For Satiety substudy population only.

(c) If time is available for an assessment on Day 1, it will be compared with dosing time on Day 1 to define Baseline value.

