5.2 Handling of Dropouts or Missing Data

Missing data will not be imputed for safety analyses. The safety evaluations will be performed on observed data only.

For AEs with partial or missing onset or stop dates:

AE stop date will be imputed first as:

- If stop date is completely missing, assume it is ongoing (no imputation);
- For a partial AE stop date (day is missing, or both day and month are missing): December 31st, or last day of the month.

Then AE onset date will be imputed as:

- If onset date is completely missing: the first dose date;
- For a partial AE onset date (day is missing, or both day and month are missing):
 - Partial date < the first dose date: December 31st, or last day of the month
 - Partial date = the first dose date: the first dose date
 - Partial date > the first dose date: January 1st, or first day of the month

If the imputed AE onset date is after the AE stop date/imputed AE stop date, then the onset date will be set to the AE stop date/imputed AE stop date.

The imputed dates will not be listed. Study day relative to the first dose of double-blind study drug associated with missing or partial dates will not be displayed in AE listings.

In the event that a partial date (month/year or year) for concomitant medication is available, this information will be used as follows:

- When both month and year are available – first day of the month will be used for start date and the last day of the month will be used for the stop date.
- When only year is available – January 1st will be used for the start date and December 31th will be used for the stop date.

The imputed dates will only be used to determine whether a concomitant medication will be classified as prior medication or concomitant medication.

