6.9.5 Diabetic Ketoacidosis

An assessment for DKA will be performed if a patient has any symptoms or signs that the Investigator believes may be consistent with DKA or if urine ketones are positive or blood BHB is >0.6 mmol/L. In these cases the Investigator will determine if an assessment for metabolic acidosis is appropriate and if yes, then the Possible DKA CRF will be completed.

Summary statistics by treatment group and overall for the actual values and change from Baseline in BHB based on central laboratory results will be provided by visit. Point-of-care BHB results will be listed. Similar summaries will be presented for urine ketones.

Cross-tabulation of A1C (using the following categories: $<7\%$, $\geq 7\%$ to $<8\%$, $\geq 8\%$ to $<9\%$, $\geq 9\%$ to $<10\%$, $\geq 10\%$, and overall) vs. BHB (using the following categories: 0, <0.2 , ≥ 0.2 , ≥ 0.3 , ≥ 0.5 , ≥ 0.6 , ≥ 1.0 , ≥ 2.0 , and ≥ 3.0 mmol/L) during Double-blind Treatment Period will be provided for each treatment group. In addition, cross-tabulation of A1C vs. urine ketones results will be presented.

Urine ketones cross-tabulated with BHB results will be presented for the Double-blind Treatment Period.

Total daily insulin, daily bolus insulin, and daily basal (or non-bolus) insulin, as percentage of the corresponding Baseline dose, will be cross-tabulated with BHB for the Double-blind Treatment Period. The insulin doses, in unit/kg, will also be cross-tabulated with BHB.

Incidence of BHB >0.6 mmol/L during the Double-blind Treatment Period will be analyzed by a logistic regression model adjusting for treatment, Baseline A1C, Baseline BHB, and age at T1D diagnosis (<18 years of age, ≥ 18 years of age). In addition, incidence of BHB >0.6 mmol/L during the Double-blind Treatment Period will be analyzed by a logistic regression model adjusting for treatment, Baseline A1C, change from Baseline to Week 24 in A1C, Baseline BHB, change from Baseline to Week 24 in mean daily basal (or non-bolus) insulin dose, and age at T1D diagnosis (<18 years of age, ≥ 18 years of age). Receiver operating characteristic (ROC) curves for assessing the accuracy of predictions will be presented for both logistic regression models. ROC curves will plot sensitivity vs. (1-specificity) for the prediction of BHB >0.6 mmol/L. The area under ROC curves as quantitative summary measures will be provided.

Box plots of BHB will be presented for Baseline and Week 24 visit by treatment group.

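### SAP 6.9.5: the second BHB model uses Week 24 changes recorded after any Week 4, 8 or 16 event, so its AUC is not predictive accuracy

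*SAP*

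**What the plan says.** SAP 6.9.5 (Diabetic Ketoacidosis) fits two logistic regressions to the same outcome, whether a patient has any BHB above 0.6 mmol/L at any time in the Double-blind Treatment Period.

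- **Model 1** adjusts for treatment, Baseline A1C, Baseline BHB and age group at diagnosis.
- **Model 2** keeps those terms and adds two changes to Week 24. Its covariate list includes "change from Baseline to Week 24 in A1C, Baseline BHB, change from Baseline to Week 24 in mean daily basal (or non-bolus) insulin dose".

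The labels Model 1 and Model 2 are mine. The section then states: "Receiver operating characteristic (ROC) curves for assessing the accuracy of predictions will be presented for both logistic regression models". The area under each curve is to be reported as a summary measure. The section sets no landmark time, no time-updated covariate and no restriction to events that follow the covariates. It does not say that Model 2 is to be read only as an association.

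Protocol 9.5.2 fixes when BHB is measured: "At every clinic visit blood BHB (central laboratory and point-of-care) testing will be conducted". Protocol 5.1.4 gives the visits: "The double-blind Treatment Period includes 5 clinic visits (Baseline, and Weeks 4, 8, 16, and 24". On missing data, SAP 5.2 says: "Missing data will not be imputed for safety analyses".

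**The concern.** A prediction model has to use information that exists before the event it predicts. In Model 2, two covariates are known only at Week 24, while the outcome can occur at any of three earlier scheduled visits.

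Ketosis bears directly on DKA, which is an adjudicated safety event and a component of the primary composite. If Model 2 shows a higher AUC than Model 1, a reader could conclude that a change in A1C or in basal insulin foretells ketosis. The plan invites that reading, because both curves carry the same prediction label.

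Two further matters follow from the same specification. Model 2's treatment term is adjusted for variables that treatment may itself alter. In addition, the two AUCs may not come from the same patients.

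**Working it through.** The SAP states no AUC, event rate or patient number for these models, so there is no planned figure to reproduce. The check is one of timing.

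**Inputs**

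- Scheduled BHB tests after Baseline: Weeks 4, 8, 16 and 24 (Protocol 5.1.4 and 9.5.2; Appendix A).
- Target days 29, 57, 113 and 169 (SAP Table 5.1-1; the last row reads "5 Week 24 | 169 | ≥142"). Only the target days are used here.
- Visit tolerance (Protocol Appendix A, footnote b): "All visit dates will be scheduled based on the date of randomization with a ± 3 days visit window allowed".
- Basal dose is not a visit-day value. It is averaged over the 3-5 days before the visit (Protocol 7.6.1.3; SAP 6.8.4.8).

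**Gap from event to covariate** = 169 − target day of the event visit. A tolerance of 3 days at each of two visits widens this by 3 + 3 = 6 days either way. For basal dose, subtract up to about 5 days.

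| Event at | Target day | Gap at target days | Gap with ±6 days | Basal dose, 5 days less |
|---|---|---|---|---|
| Week 4 | 29 | 169 − 29 = 140 days (20 weeks) | 134 to 146 | about 135 |
| Week 8 | 57 | 169 − 57 = 112 days (16 weeks) | 106 to 118 | about 107 |
| Week 16 | 113 | 169 − 113 = 56 days (8 weeks) | 50 to 62 | about 51 |
| Week 24 | 169 | 0, same visit | – | dose days just before the test |

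For three of the four scheduled tests, the Week 24 values come weeks after the BHB result. For the fourth they are roughly concurrent. The order is the same whether visits are assigned by the analysis windows or by nominal visit, because Week 24 follows Weeks 4, 8 and 16 either way.

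**Treatment term.** Changes in A1C and basal dose arise after randomization. Conditioning on them removes any part of the treatment effect that runs through them, and may open other paths. Model 2's treatment odds ratio is therefore not the total effect. Model 1 conditions only on baseline terms.

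**Reverse causation.** Insulin is adjusted during the study: "The need for insulin adjustments will be evaluated by the Investigator with the goal of maintaining or improving glycemic control" (Protocol 7.6.1.5). A ketosis episode could therefore be followed by dose changes that show up at Week 24. However, the response to ketosis described in Protocol 9.5.2 and Appendix F is rapid-acting insulin, and no lasting basal change is described.

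**Patient sets.** With no imputation in safety analyses, a patient who lacks a Week 24 A1C or insulin value can enter Model 1 but not Model 2.

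**The case against.** **It is only descriptive.** The protocol calls safety analysis descriptive, Model 2 is introduced as an addition, and nothing says its treatment term will be reported as a treatment effect. This limits the consequence. It does not cure the wording, because the same paragraph attaches a prediction purpose to Model 2 by name.

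**An AUC measures discrimination, and Model 1's is in-sample too.** That is true: no validation is planned for either model. But Model 1's covariates exist before the events, so its AUC can at least be read as apparent predictive accuracy. Model 2's cannot, however it is validated.

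**Week 24 change may stand in for earlier change.** No stand-in is needed, since A1C, insulin and BHB are all collected at Weeks 4, 8 and 16.

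**Patients who stop drug can remain in follow-up** (Protocol 6.3.3) and so have Week 24 values. This stands: the two patient sets may differ, but by how much is unknown. Counts per model may also appear in the table shells, which are held in a separate file.

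Some stronger readings are tempting but not supported:

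- *Most events precede Week 24.* The documents give no BHB event rate by visit, so any share would rest on invented risks.
- *Exact minimum gaps follow from the analysis windows.* SAP 5.1 applies those windows to by-visit endpoint analyses and uses nominal visits elsewhere. It is not clear that they govern this period-level model.
- *Model 2's insulin odds ratio reflects reverse causation.* The stated ketosis response is not basal insulin, and A1C is masked after randomization unless it exceeds 11.0% from Week 16. Feedback is possible, not shown.

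**Conclusion.** The concern holds for Model 2 only. As written, the plan would report a prediction accuracy that the model cannot have, because two covariates are recorded about 20, 16 or 8 weeks after a Week 4, 8 or 16 event (up to about 5 days less for basal dose) and at about the same time as a Week 24 event. Its treatment odds ratio is not a total treatment effect. Any bias in the AUC or odds ratios cannot be sized or signed from the documents.

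The gaps assume that visits fall on their target days and that events are detected at scheduled tests. They do not depend on any assumed event rate.

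The stakes are limited. Model 1 is unaffected. SAP section 7 lists these regressions as added to the protocol's analyses, and they lie outside the testing sequence in SAP 6.8, so a reader should not infer any weakness in the primary or secondary results. What changes is what may be said about predictors of ketosis.

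**What to change.** In SAP 6.9.5:

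1. Limit the ROC curve and AUC presented as prediction accuracy to Model 1.
2. Take the treatment odds ratio from Model 1.
3. Label Model 2 a descriptive association. The cross-tabulations and scatter plots of BHB against A1C and insulin in the same section already serve that purpose.

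This costs a few words and the loss of Model 2's AUC figure. Showing the number of patients and events behind each model would help a reader but is an extra.

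If prediction by A1C or insulin change is wanted, fit a visit-level model up to the first BHB above 0.6 mmol/L. For each BHB assessment, use the A1C and basal dose from the preceding visit, with Baseline values for Week 4. This needs modest programming and no new data. Its limits should be stated: home BHB readings between visits may still influence dosing, and its treatment odds ratio would not be the total effect either.

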6.9.6 Acidosis-related Adverse Events

Incidence of treatment-emergent acidosis-related AEs will be summarized to include patient counts and percentages by treatment group, and by use of CSII at Screening (Yes, No) as well, for the following: (serious and non-serious) acidosis-related AEs, serious acidosis-related AEs, non-serious acidosis-related AEs, positively adjudicated metabolic acidosis, and positively adjudicated metabolic acidosis that were also DKA.

Acidosis-related AEs are those that satisfy the trigger terms for metabolic acidosis defined in the table below. All acidosis-related AEs were adjudicated for metabolic acidosis. All cases of positively adjudicated metabolic acidosis were then adjudicated for the presence or absence of DKA.

| Trigger Terms for Metabolic Acidosis | |
|--|---|
| Trigger Terms Typically Associated With Elevated BHB | Trigger Terms That May Not Be Associated with Elevated BHB |
| Acetonaemia | Acidosis Hyperchloraemic |
| Blood Ketone Body | Metabolic Acidosis |
| Blood Ketone Body Increased | Lactic Acidosis |
| Blood Ketone Body Present | Renal Tubular Acidosis |
| Diabetic Ketoacidosis | Acidosis |
| Diabetic Ketoacidotic Hyperglycemic Coma | Uraemic Acidosis |
| Ketoacidosis | Diabetic Coma |
| Urine Ketone Body | Diabetic Hyperglycemia Coma |
| Urine Ketone Body Present | Diabetic Metabolic Decompensation |
| | Hyperglycemic Coma |
| | Hyperglycemic Seizure |
| | Hyperglycemic Unconsciousness |

The trigger terms correspond to MedDRA PTs. All trigger terms in both columns of the table will be included in the search for acidosis-related AEs, without regard to the presence or absence of an associated elevated BHB value.

6.9.7 Drug-induced Liver Injury Events

Summaries by treatment group for liver safety laboratory abnormalities will be provided based on the Investigator-reported and positively adjudicated data, and laboratory data.

The incidence of liver enzyme or bilirubin abnormalities will be summarized by treatment group based on laboratory data regardless of the Investigator reports. The number and percentage of patients with post-

Statistical Analysis Plan

Version: Final 1.0

Lexicon Pharmaceuticals Protocol No. LX 4211.1-312-T1DM

Date of Issue: 17 MAR 2017

Covance Study ID: 000000145143

Baseline elevation of alanine aminotransferase (ALT), aspartate aminotransferase (AST), and bilirubin according to various multiples of the upper limit of normal (ULN) will be presented:

- ALT >3xULN, >5xULN, >8xULN, >10xULN, >20xULN
- ALT >3xULN and total bilirubin >2xULN
- AST >3xULN, >5xULN, >8xULN, >10xULN, >20xULN
- AST >3xULN and total bilirubin >2xULN
- ALT or AST >3xULN, >5xULN, >8xULN, >10xULN, >20xULN
- ALT >3xULN and total bilirubin >2xULN or AST >3xULN and total bilirubin >2xULN
- ALT and AST >3xULN, >5xULN, >8xULN, >10xULN, >20xULN
- ALT >3xULN and total bilirubin >2xULN and AST >3xULN and total bilirubin >2xULN

All analyses described above will be performed for the Safety population.

Scatter plots of maximum ALT vs. maximum total bilirubin and maximum AST vs. maximum total bilirubin per patient will be presented. Maximum values are presented by number of multiples of ULN.

A patient listing will be presented for those patients with Investigator-reported abnormalities and corresponding adjudication results. A patient listing of laboratory results of liver enzyme and bilirubin abnormalities will be presented for DILI events.

